Methodology:	The testing methods are based on the standardized test method ASTM E1173-15, Evaluation of Preoperative, Precatheterization, or Preinjection Skin Preparations . Following a 14-day restriction period, subjects will be sampled for baseline, 30-seconds, 10-minutes, and 6-hours microbial reduction evaluations post-product application. Subjects will be sequestered for the 6-hour evaluation. Test day baseline criteria will be set at: abdomen: $3.0 - 5.5 \log_{10} \text{CFU/cm}^2$, and inguen: $5.0 - 7.5 \log_{10} \text{CFU/cm}^2$.
Number of Subjects:	A sufficient number of subjects will be entered into testing to complete 50 subjects per each of the 2 test and 1 control materials. A minimum of 75 subjects meeting the test day baseline criteria will test bi-laterally (150 abdomen and inguinal sites; 50 abdomen and inguinal sites per test and control materials).
Main Criteria for Inclusion:	A sufficient number of overtly healthy subjects at least 18 years of age will be admitted into the study so that a minimum of 75 subjects complete the study. Insofar as possible, the groups of subjects selected will be of mixed sex, age, and race. The subject recruiters will verbally and/or visually verify with subjects that the skin of the abdomen and inguen are free from clinically evident dermatoses, injuries, or any other disorders that may compromise the subject or the study.
Duration of treatment:	For each subject, two of the three test materials will be applied bi-laterally to abdomen and inguinal sites, a single time.

Name of Sponsor: Professional Disposables International, Inc. (PDI)	
Name and Concentration of Test Product Active Ingredients: 26 mL Chlorhexidine Gluconate 3.15% (w/v) and Isopropyl Alcohol 70% (v/v) solution 5.1 mL Chlorhexidine Gluconate 3.15% (w/v) and Isopropyl Alcohol 70% (v/v) solution	Protocol Number 1810480-103.01

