
Statistical Methods:
	
A statistical analysis of the data will be performed to determine the non-inferiority of the two test products to the Positive Control. Separate analyses will be performed for data sets for the abdomen and the inguinal test sites and for the 30-seconds and 10-minutes post-application sample times. The statistic to be used is a multiple linear regression with one quantitative and one qualitative variable. The average treatment effect (ATE) is the mean difference of the two products with the 95% confidence intervals in place that will determine if the test products will pass the non-inferiority evaluation. To pass, the upper bounds of the 95% confidence interval must be equal to or less than $0.5 \log_{10}$. The number of subjects necessary to pass this requirement will be determined.
 
Descriptive statistics will be generated, including sample sizes, means, standard deviations, and ranges.

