9.0 INVESTIGATIONAL PLAN

9.1 Overall Study Design and Plan

This pilot study is designed to determine the antimicrobial effectiveness of two test products (Test Products #1 and #2), intended for use as Patient Preoperative Skin Preparations. The testing methods are based on the standardized test method ASTM E1173-15, *Evaluation of Preoperative, Precatheterization, or Preinjection Skin Preparations*, and using the requirements specified by the 2017 FDA 21 CFR Part 310, *Safety and Effectiveness of Health Care Antiseptics; Topical Antimicrobial Drug Products for Over-the-Counter Human Use*, Final Rule (December 20, 2017). The immediate and persistent antimicrobial effects will be measured to evaluate the efficacy.

At least 75 subjects will be treated bilaterally with two of the three test materials (Test Product #1, Test Product #2, and Positive Control), one per each side of the abdomen and inguinal test sites. Subjects will be required to complete a 14-day pre-test conditioning period. Subjects will complete a 1-day test period, during which time subjects' sites will be treated with the test materials and samples taken following treatment. The Cylinder Sampling Technique will be performed for baseline and for sampling 30-seconds, 10-minutes, and 6-hours post-test material-application on Test Day.

The effectiveness criteria are that the \log_{10} recoveries of the two test products (26 mL and 5.1 mL) are non-inferior to the Positive Control (Prevantics® Maxi Swabstick 5.1 mL) with a 0.5 margin (\log_{10} scale) per square centimeter on the abdominal and inguinal sites within 30 seconds after drying and within 10 minutes after drying. The determination of non-inferiority will be based on the upper bounds of the 95% confidence interval being equal to or less than 0.5. Superiority will not be evaluated in this study. To show persistence for the test materials, the 6 hours post-treatment measurement should be lower than or equal to the baseline measurement for microbial reductions for 100 percent of the subjects on the abdominal and inguinal sites. This evaluation will determine the correct application procedures and the power for the pivotal study.

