9.3 Selection of Study Population

A sufficient number of overtly healthy subjects at least 18 years of age will be admitted into the study so that 50 abdomen and 50 inguinal site evaluations are completed per each test material at each post-treatment sample time from sites passing Treatment Day baseline criteria (3.0 - 5.5 \log_{10} CFU/cm² from the skin of the abdomen and 5.0 - 7.5 \log_{10} CFU/cm² from the skin of the inguen). Insofar as possible, the group of subjects selected will be of mixed gender, age, and race. All subjects will be free from clinically evident dermatoses, injuries, wounds, and/or any other disorders that may compromise the subject and the study. All subjects will sign the Informed Consent Form and List of Restricted Products prior to participating in the study. The above forms are provided as separate Informed Consent documents. Subjects will receive a copy of these documents once consented to the study. Subjects must also have a current Authorization to Use and Disclose Protected Health Information Form on file at the testing facility. The Informed Consent Form will include a list of the active ingredients and post study product-removal

materials to which subjects may be exposed. The Informed Consent Form provides the subject with contact information for the Principal Investigator, and Subinvestigator(s), as appropriate.

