9.4.3 Method of Assigning Subjects to Treatment Groups

The three test materials will be assigned randomly to the test sites per a computer-generated randomization schedule, such that two of the three test materials are used on each subject at the abdomen and/or inguinal sites, one test material on one side, and another test material on the opposite side of the subject. The randomization schedule will be continued until it is determined that the required sample sizes are fulfilled.

The specific sites for post-application sampling (i.e., 30 seconds, 10 minutes, and 6 hours after skin preparation on the abdominal and inguinal test sites) will be assigned according to a computer-generated randomization scheme.

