9.5.3 Primary Efficacy Variables

The primary efficacy variables for this study are the immediate antimicrobial effects at 30-seconds and 10-minutes post-application and persistent antimicrobial effects at 6-hours post-application. The effectiveness criteria are that the \log_{10} recoveries of the two test products (26 mL and 5.1 mL) are non-inferior to the Positive Control (Prevantics® Maxi Swabstick 5.1 mL) with a 0.5 margin (\log_{10} scale) per square centimeter on the abdominal and inguinal sites within 30 seconds after drying and within 10 minutes after drying. The determination of non-inferiority will be based on the regression model used with a 95% confidence interval around the Average Treatment Effect (ATE). The upper bound of the 95% confidence interval cannot exceed 0.5. To show persistence of effect for the test materials, the 6-hours post-treatment measurement should be lower than or equal to the baseline measurement for 100 percent of the subjects on the abdominal and inguinal sites. The efficacy criteria will be consistent with the requirements of the 2017 FDA 21 CFR Part 310, *Safety and Effectiveness of Health Care Antiseptics; Topical Antimicrobial Drug Products for Over-the-Counter Human Use*, Final Rule (December 20, 2017).

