9.7.1 Statistical Methods

The Minitab® Version 18 statistical computer package will be used for all statistical calculations.

Non-Inferiority Analysis

An analysis of the data will be performed to determine the non-inferiority of the two test products to the Positive Control. Separate analyses will be performed for data sets for both the abdomen and the inguinal test sites and for the 30-seconds and 10-minutes post-application sample time. Only those data from sites meeting the baseline criteria (3.0 - 5.5 \log_{10} CFU/cm² from the skin of the abdomen and 5.0 - 7.5 \log_{10} CFU/cm² from the skin of the inguen) will be used in the analysis.

The statistic to be used is a multiple linear regression with one quantitative and one qualitative predictor. It has the form:

$$\hat{y} = B_0 + B_1 x_1 + B_2 x_2 + e$$

where:

\hat{y} = \log_{10} Recoveries

B_0 = y intercept

B_1 = Regression slope

B_2 = Difference between the two products

x_1 = \log_{10} Baseline

x_2 = Products

1, if Test Product

2, if Positive Control

e = Error term

The average treatment effect (ATE) is the mean of the 95% confidence interval. For the non-inferiority test, the upper bound of the 95% confidence interval must be equal to or less than 0.5 \log_{10} .

For the non-inferiority test:

$$\bar{x}_C - \bar{x}_T \leq 0.5$$

where:

\bar{x}_T = mean of the test product

\bar{x}_C = mean of the positive control product

0.5 = non-inferiority margin

Descriptive statistics will be generated, including sample sizes, means, standard deviations, and ranges of the recovery data.

Sample Size Determination Analysis

When the study is complete, the PASS 16 statistical package will determine the number of subjects used in a pivotal study for the abdominal and inguinal regions.

The formula that will be used is:

$$n \geq \frac{2 s^2 (z_{\alpha/2} + z_{\beta})^2}{0.5^2}$$

where:

n = minimum number of subjects employed in the study

2 = number of products tested; 3 test materials (Test Product #1, Test Product #2 and Positive Control)

s^2 = the largest variance of the two products tested at the abdominal or inguinal sites

$z_{\alpha/2} = 1.96$ (z-scale) for $1 - 0.05 = 95\%$ confidence of Type I error

$z_{\beta} = 0.842$ (z-scale) for $1 - 0.20 = 0.80\%$ confidence of Type II error

0.5 = Detection level requirement

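### The non-inferiority regression treats the two sides of one subject as independent, so its 95% confidence interval has the wrong width if their residuals are correlated (too wide if the correlation is positive)

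*Combined protocol and SAP*

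**What the plan says.** The design is within-subject. The synopsis (Duration of treatment) says "For each subject, two of the three test materials will be applied bi-laterally to abdomen and inguinal sites, a single time", and section 9.4.3 puts "one test material on one side, and another test material on the opposite side of the subject". Section 9.1 repeats it: "At least 75 subjects will be treated bilaterally with two of the three test materials". On numbers, the synopsis says "A minimum of 75 subjects meeting the test day baseline criteria will test bi-laterally", and section 9.3 asks that "50 abdomen and 50 inguinal site evaluations are completed per each test material".

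The analysis is described in section 9.7.1: "The statistic to be used is a multiple linear regression with one quantitative and one qualitative predictor". The outcome is log10 recovery. The predictors are log10 baseline and a product indicator that distinguishes one test product from the positive control. There is one error term. The model is run separately for each body region and for the 30-second and 10-minute samples. The synopsis gives the same model.

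The pass rule is the upper confidence limit. The synopsis says "To pass, the upper bounds of the 95% confidence interval must be equal to or less than" 0.5 log10, and section 9.5.3 says "The upper bound of the 95% confidence interval cannot exceed 0.5".

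No section mentions a subject or block term, a paired analysis, a mixed model or a cluster-robust variance.

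**The concern.** Running the analyses separately by region and time point does not separate subjects. Within one fit, a subject assigned both the test product and the control supplies two rows, and the regression treats them as if they came from two people. Adjusting for each site's own baseline may remove some of what the two sides share. Whatever remains is a residual correlation, called rho here.

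The estimated product difference is unbiased at any rho. Its standard error is too large if rho is positive, correct if rho is 0 and too small if rho is negative. Because the upper limit of the interval is the pass criterion, positive rho produces false fails and lost power. Negative rho pushes the one-sided error above the nominal 2.5%.

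**Working it through.** **Inputs from the documents.** 75 subjects with two sites each per region; 50 sites per material; margin 0.5 log10; 95% interval, taken as two-sided (z = 1.96, one-sided 2.5%).

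**Assumed, because the documents do not give them.** Residual SD s after baseline adjustment (1 log10, range 0.7 to 1.25) and rho (−0.2 to 0.5).

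**Step 1: the plan's own figure.** 75 × 2 / 3 = 50 sites per material, as stated.

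**Step 2: pairing.** Let a, b and c be the numbers of subjects with Test 1 and control, Test 2 and control, and Test 1 and Test 2. Then a + c = b + c = a + b = 50, so a = b = c = 25. Half of the 50 test sites in each comparison share a subject with a control site.

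**Step 3: reported and true variance of the product difference.**
- Reported: 2s²/50 = 0.040s², whatever rho is.
- True: 0.040s² − 2 × 25 × rho × s²/50² = 0.040s²(1 − rho/2).

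Excess width is √(reported/true) − 1, coverage is 2Φ(1.96√(reported/true)) − 1, and one-sided error is 1 − Φ(1.96√(reported/true)).

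| rho | true variance / s² | planned interval | coverage | one-sided error |
|---|---|---|---|---|
| −0.2 | 0.044 | 4.7% too narrow | 93.83% | 3.1% |
| 0 | 0.040 | correct | 95.00% | 2.5% |
| 0.1 | 0.038 | 2.6% too wide | 95.57% | 2.2% |
| 0.2 | 0.036 | 5.4% too wide | 96.12% | 1.9% |
| 0.3 | 0.034 | 8.5% too wide | 96.65% | 1.7% |
| 0.5 | 0.030 | 15.5% too wide | 97.64% | 1.2% |

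**Step 4: chance of passing one comparison when there is no true difference.**
- Planned: Φ((0.5 − 1.96 SE_reported)/SE_true).
- Same estimate with the correct standard error: Φ(0.5/SE_true − 1.96).
- Three-material model with a subject effect and known rho: Φ(0.5/SE_GLS − 1.96), where the variance is 0.16s²/[3/(1 − rho) + 1/(1 + rho)]. This gives 0.0377s², 0.0317s² and 0.0240s² at rho 0.1, 0.3 and 0.5.

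Example at s = 1 and rho 0.3: SE_reported = 0.200 and SE_true = √0.034 = 0.184. Planned is Φ(0.108/0.184) = 72%, corrected is Φ(0.5/0.184 − 1.96) = 77%, and the three-material model gives 80%.

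| s | rho | planned | correct SE | three-material model |
|---|---|---|---|---|
| 1 | 0.1 | 71% | 73% | 73% |
| 1 | 0.3 | 72% | 77% | 80% |
| 1 | 0.5 | 73% | 82% | 90% |
| 0.7 | 0.3 | 96% | 97% | 98% |
| 0.7 | 0.5 | 97% | 98% | 99.6% |
| 1.25 | 0.3 | 52% | 58% | 61% |
| 1.25 | 0.5 | 52% | 64% | 73% |

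The step from planned to correct SE is the error itself. The further step is efficiency from a better estimator. The last column is an upper bound, because it takes rho as known and uses 1.96.

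**Step 5: simulation with rho estimated.** There were 10,000 runs per setting, with s = 1, REML and Satterthwaite degrees of freedom. Baseline SD was assumed to be 0.6, left-right baseline correlation 0.5 and slope 0.3. Planned to mixed pass chance was 70% to 73% (rho 0.1), 71% to 79% (0.3) and 72% to 89% (0.5). At rho 0 both gave 70%. Planned coverage was 93.7% at rho −0.2 and 97.7% at 0.5. Mixed-model coverage stayed between 94.4% and 95.4% over all settings.

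**Step 6: broken pairs.** Section 9.7.1 excludes by site, so some subjects may lose one side. Suppose one third do: 60 intact subjects (20 per pair) and 30 one-sided (10 sites per material). True variance is then 0.0352s² and 0.0320s² at rho 0.3 and 0.5, and coverage is 96.3% and 97.2%. The three pass chances at s = 1 are 72%, 76%, 79% and 73%, 80%, 87%.

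**Step 7: pivotal sizing.** The section 9.7.1 formula is 2s²(1.96 + 0.842)²/0.5² = 62.8s². It uses the variance directly, so the wrong interval width does not enter it. Read as a number per material, it exceeds the 100-per-material minimum in sections 9.2 and 9.7.2 only if s is above √(100/62.8) = 1.26. That section does not say its variance is baseline-adjusted, so the threshold is approximate.

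**The case against.** The strongest reply is that the error is harmless in the likely direction. For any rho of zero or more the interval is too wide, so the study cannot wrongly declare non-inferiority because of it, and nothing in the documents points to negative rho. The pilot's declared aims are application procedures and pivotal sizing, and the sizing formula is untouched. At 100 sites per material, s = 1, rho 0.3 and the same layout, the reported SE is √0.020 = 0.141 and the true SE is √0.017 = 0.130. The pass chance moves only from 95.6% to 97.0%. Baseline adjustment may leave little correlation, and a value of 0.5 after adjustment has no support in the documents. Finally, a subject effect in the planned two-product model would be a narrower cure. It gives 79% and 87% at rho 0.3 and 0.5, against 80% and 90% for the three-material model.

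Much of this stands. The size depends wholly on assumed values, the direction is conservative for positive rho, and only the SE-correction step should be counted as the defect. It does not remove the point. Sections 9.1 and 9.5.3 still set a pass/fail criterion for the pilot, and section 9.7.2 uses the pilot to judge whether a pivotal study is likely to succeed. False fails work against both. The synopsis ties the planned regression to the cited Final Rule, which is a reason to keep showing it but not to leave the pairing out.

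**Conclusion.** The concern holds. The planned model ignores a within-subject pairing that the design builds in, and the interval it produces is the decision rule. The mechanism is certain; the size is conditional on rho and s. With 25 intact pairs per comparison, the planned interval is right at rho 0, 8.5% too wide at 0.3 and 15.5% too wide at 0.5. At s = 1 this costs about 5 and 9 percentage points of pass chance through the standard error alone. The cost is small at rho 0.1 (71% against 73%) or at s = 0.7 (1 to 2 points at rho 0.3 and 0.5). Only negative rho inflates the error, to 3.1% at −0.2. The effect falls on the pilot's own pass/fail result, so this is a change that should be made rather than one that invalidates the study.

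**What to change.** Amend section 9.7.1 before the data are analysed. For each region and each of the two time points:

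- Fit one linear mixed model to all three materials, with log10 recovery on log10 baseline and a three-level product factor. Use REML and Kenward-Roger or Satterthwaite degrees of freedom.
- Include a random subject effect or, so that negative correlation is allowed, an unrestricted within-subject covariance.
- Take both test-versus-control contrasts and their 95% intervals from this model. State the contrast direction and reconcile it with the control-minus-test expression and the 1/2 product coding now in section 9.7.1. The widths, and the pass chances at zero difference, are the same in either direction.
- Report the within-subject correlation and the residual variance, which also inform pivotal planning.
- Show the planned regression alongside.

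The cost is a written amendment to the institutional review board under section 9.8, a check that the statistical package named in section 9.7.1 can fit the model, and slightly more analysis work. No new data are needed. If the residual correlation proves to be near zero, the results will be essentially unchanged.

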9.5.1 Efficacy and Safety Measurements and Flow Chart

Mean log₁₀ reductions in normal flora will be used to determine the antimicrobial effectiveness of the test materials.

Flow Chart

Procedure	Day		
	-14 or more	-14 to 0	0
Informed Consent Signed	X		
Inclusion/Exclusion Criteria Reviewed	X		X
Pre-Test Conditioning Period		X	
Evaluation of Skin Condition			X
Test Material Application Locations and Sampling Sites Assigned			X
Baseline Sample			X
Test Material Application			X
30-second Post-Application Sample			X
10-minute Post-Application Sample			X
6-hour Post-Application Sample			X

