9.5.4 Data Collection and Microbial Recoveries

Colonies will be manually counted and data recorded on appropriate data collection forms. If one of the plates is uncountable, the count on the remaining plate will be used for calculations and noted in the source record.

The estimated \log_{10} number of viable microorganisms recovered from each sample site will be designated the “R-value.”

To convert the volumetric measure of the sample into the number of colony-forming units per square centimeter (cm^2), the following formula will be employed:

$$R = \log_{10} \left[\frac{F \left(\frac{\sum c_i}{n} \right) 10^{-D}}{A} \right]$$

where:

R = the average colony-forming unit count in \log_{10} scale per cm^2 of sampling surface

F = total number of mL of stripping fluid added to the sampling cylinder; in this study, $F = 6 \text{ mL}$

$$\frac{\sum c_i}{n} = \text{average of the triplicate colony counts used for each sample collected}$$

D = dilution_factor of the plate counts

A = inside area of the cylinder in cm^2 ; in this study, $A = 3.46 \text{ cm}^2$

NOTE: The reason that a \log_{10} transformation will be performed on the collected data is to obtain a linear scale. A linear scale, more appropriately a \log_{10} linear scale, is a basic requirement of the statistical models used in this study.

Average colony counts ($\frac{\sum c_i}{n}$) of 0 will be set to 0.5 prior to calculating R -values. Any

calculated CFU/cm^2 values ($\frac{F(\frac{\sum c_i}{n})10^{-D}}{A}$) of less than 1 will be set to 1 CFU/cm^2 , such that the \log_{10} transformation will be zero for the calculated R -Value.

Data collected from subjects with low or high test-day baseline counts on an anatomical test site ($< 3.0 \log_{10} \text{CFU}/\text{cm}^2 > 5.5 \log_{10} \text{CFU}/\text{cm}^2$ from the skin of the abdomen, or $< 5.0 \log_{10} \text{CFU}/\text{cm}^2 > 7.5 \log_{10} \text{CFU}/\text{cm}^2$ on the skin on the inguen) will not be used in the Efficacy Analyses (Section 9.7.1). This is a common occurrence in clinical-simulation studies. Hence, more subjects will be enrolled and tested to account for test-day baseline failures.

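### The non-inferiority rule in 9.7.1 is set on Control minus Test although the response is log10 recoveries, so as written an inferior product passes and a much better one fails

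*Combined protocol and SAP*

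**What the plan says.** Section 9.7.1 (Non-Inferiority Analysis) specifies a linear regression of log10 recoveries on log10 baseline and product. The product variable is coded "1, if Test Product" and "2, if Positive Control". Its coefficient B2 is described only as "Difference between the two products". The decision rule is "For the non-inferiority test, the upper bound of the 95% confidence interval must be equal to or less than" 0.5 log10. The condition displayed beneath it is the positive-control mean minus the test-product mean, at most 0.5.

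Two other sections fix the direction of the scale. Section 9.5.4 defines the recovery value: "R = the average colony-forming unit count in" log10 scale per square centimetre of skin sampled. Section 9.5.3 sets persistence so that low values are good: "the 6-hours post-treatment measurement should be lower than or equal to the baseline measurement for 100 percent of the subjects".

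The synopsis (Criteria for Evaluation) and Sections 9.1, 9.5.2 and 9.5.3 all state the non-inferiority criterion on log10 recoveries, with the same 0.5 margin. Section 9.5.1 differs. It says that mean log10 "reductions in normal flora will be used to determine the antimicrobial effectiveness of the test materials".

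**The concern.** When the response is surviving organisms, non-inferiority means that the test product leaves at most 0.5 log10 more than the control. That requires an upper limit on Test minus Control. Section 9.7.1 puts the upper limit on Control minus Test, which is the form that suits log10 reductions.

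This is the primary pass/fail rule. It is applied to two test products, two body regions and two sampling times, which makes eight comparisons. Its results are used to judge whether a pivotal study with 100 subjects per material is likely to succeed (Sections 9.2 and 9.7.2). An analyst who programs the stated response, coding and bound gets the reversed contrast.

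**Working it through.** The plan gives no SD or power for the non-inferiority test, so there is no figure of its own to reproduce.

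**Sign of the contrast**

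1. Response: log10 recoveries, higher is worse (9.7.1, 9.5.4).
2. The model is y = B0 + B1·x1 + B2·x2 + e, with x2 = 1 for Test and 2 for Control. At equal baseline, mean(Control) − mean(Test) = B2·(2 − 1) = B2. So B2 is Control minus Test.
3. The displayed inequality is also Control minus Test. Following the regression instead of the display therefore gives the same reversed contrast.
4. Reduction = baseline − recovery. With baseline already in the model, changing the response from recovery to reduction reverses the sign of B2. Control minus Test with an upper bound of 0.5 is thus right for reductions (9.5.1) and wrong for recoveries (9.7.1).

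**Size**

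Inputs: 50 sites per material (synopsis; 75 subjects × 2 sides / 3 materials = 50), margin 0.5, two-sided 95% interval (1.96). The SD is assumed to be 0.8, 1.0 or 1.2 log10. Sites are treated as independent.

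Let d be the true Test minus Control difference in log10 recoveries, and SE = SD·√(2/50) = 0.2·SD, i.e. 0.16, 0.20 and 0.24.

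- As written: P(pass) = Φ((0.5 + d)/SE − 1.96)
- Test minus Control: P(pass) = Φ((0.5 − d)/SE − 1.96)

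Example with SD 1.0 and d = +0.5. As written: Φ(1.0/0.20 − 1.96) = Φ(3.04) = 0.9988. Test minus Control: Φ(0 − 1.96) = 0.025.

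| True d (SD 1.0) | Passes as written | Passes on Test minus Control |
|---|---|---|
| +1.0 (test worse) | >99.9% | <0.1% |
| +0.5 (worse by the margin) | 99.9% | 2.5% |
| 0 | 70.5% | 70.5% |
| −0.5 (test better) | 2.5% | 99.9% |
| −1.0 | <0.1% | >99.9% |

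At d = +0.5 the written rule passes Φ(1.0/0.16 − 1.96) = Φ(4.29), over 99.9%, for SD 0.8, and Φ(1.0/0.24 − 1.96) = Φ(2.21) = 98.6% for SD 1.2. Even at SD 1.5 it passes 91.5%. At d = −1.0 and SD 1.2 it passes Φ(−0.5/0.24 − 1.96) = Φ(−4.04), below 0.01%.

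In terms of the interval at SD 1.0 (half-width 1.96 × 0.20 = 0.392): an observed difference of 1.0 log10 worse gives an upper limit of −1.0 + 0.392 = −0.61, a pass. An observed difference of 1.0 better gives 1.0 + 0.392 = 1.39, a fail.

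**Check by simulation**

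The stated regression with the 1/2 coding was simulated 4,000 times (50 per product, SD 1.0). For a product worse by 1.0, the mean B2 was −1.00 and 100% passed. For a product better by 1.0, the mean B2 was +1.01 and none passed. At d = +0.5, 99.8% passed as written and 2.9% with the sign corrected.

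**At zero true difference**

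The two rules then have the same pass probability, but they need not give the same verdict in a given dataset. Both pass only if the observed difference lies within ±(0.5 − 1.96·SE), which is ±0.108 at SD 1.0. Otherwise exactly one passes. The chance of opposite verdicts is 2 × (1 − 0.7054) = 59% at SD 1.0. The same calculation gives 24% at SD 0.8 and 90% at SD 1.2.

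**The case against.** The strongest reply is that the intent is plain. The synopsis and Sections 9.1, 9.5.2 and 9.5.3 ask for test recoveries non-inferior to control within 0.5. The synopsis names the test product before the control when it describes the ATE, and no section equates the ATE with B2. The displayed means are not labelled as recoveries or reductions, and on the reduction scale of 9.5.1 the inequality is correct. A careful statistician might simply put the sign right. All three materials list the same active ingredients at the same concentrations (9.4.2), so differences of 1.0 log10 are only illustrations. The study is a pilot, and neither the sample-size formula nor the 6-hour criterion contains the contrast.

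Much of this stands as context. The pivotal sample-size formula and the persistence criterion are unaffected, the pass rates assume literal application, and the verdict is not reversed in every dataset. The reply does not remove the error. Word order in the synopsis does not define a contrast, and 9.7.1 is the only place that gives one. The response named in that section is recoveries, and its coding and display agree with each other in the wrong direction. A silent correction would depart from the written primary rule, and would be post hoc if made after the data were seen. Similar products do not make it harmless either: at zero true difference, the two rules often disagree in a given dataset.

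**Conclusion.** The concern holds. Read as written, the primary rule limits how much better a test product may be and sets no limit on how much worse. A product worse by exactly the margin would pass 98.6% to over 99.9% of the time instead of 2.5%.

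These rates rest on 50 independent sites per material, a normal approximation and an assumed SD of 0.8 to 1.2 log10. Allowing for pairing within subjects would change the SE and so the rates, but not the sign. The direction follows from the text alone. A formula carried over from an analysis of log10 reductions is the likely origin, but that is an inference. The rule must be corrected before any data are analysed.

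**What to change.** In 9.7.1, keep log10 recovery as the response and code Control = 0, Test = 1. B2 is then the baseline-adjusted Test mean minus Control mean. State that the ATE is B2, in place of the present description of it as the mean of the confidence interval. Replace the displayed inequality, which compares means and not a confidence limit, by: upper limit of the 95% confidence interval for B2 ≤ 0.5. Make 9.5.1 name log10 recoveries, and give the same signed definition of the ATE in the synopsis and 9.5.3.

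An equivalent alternative is to make log10 reduction the response throughout and keep Control minus Test. That needs more edits, because the criteria in the synopsis, 9.1, 9.5.2 and 9.5.3 all name recoveries.

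The cost is wording only, with no change to subjects, samples or procedures. Section 9.8 does require agreement of the parties and a written amendment approved by the review board before it is implemented.
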